Appendix

Table 2 WHO data registration items

Data category	Information					
Protocol version	Version 1 - 21 January 2021					
Primary Registry	Clinicaltrial.gov					
Date of Registration	12-03-2018					
Sources of Monetary	Danish Health Authority, Danish Rheumatism Association					
Primary Sponsor	Department of Neurology, Hospital South West Jutland, Esbjerg Denmark					
Secondary Sponsor	Research Unit of Health Sciences, Hospital South West Jutland, Esbjerg Denmark					
Contact for Public Queries	[name]					
Contact for Scientific Queries	[name]					
Country of Recruitment	Denmark					
Health Condition	Osteoarthritis (DM17)					
Interventions	Cryoneurolysis					
	Sham					
	GLA:D					
Key inclusion and exclusion criteria	Inclusion: Referred to GLA:D, Chronic pain > 6 months, Pain intensity ≥40 mm on the NRS pain scale, OA confirmed by radiography, 50% reduction of pain after diagnostic nerve block					
	Exclusion: Systemic inflammatory disease, In treatment for other pain conditions, uncontrolled serious disease (cancer, diabetes, etc.)					
Study type	Interventional					
	Allocation; Randomized controlled; Parallel assignment; Single-blinded (patients and data-manager)					
	Primary purpose; Safety and effectiveness					
Date if first enrollment	26-06-20,189					
Sample size	n = 94					
Recruitment status	Recruiting					
Primary outcome	Change in Pain intensity score (NRS) after cryoneurolysis, compared between intervention and sham					
Key secondary outcomes	Functional performance					
	Quality of Life					
	Adverse effects					

training at home. These factors might confound the outcome of the exercise program but is consistent with clinical practice. The primary investigator facilitates GLA:D participation.

Strength and limitations

This study is a blinded randomized controlled sham trial that includes long-term follow ups allowing for an evaluation of the long-term effects of treatment. The sham intervention includes the same procedures as in cryoneurolysis treatment, emulating both physical marks and sensory experiences such as sound and vision. Despite of this, some performance bias cannot be excluded, and some attrition bias might occur, due to patients seeking treatment elsewhere – expectedly from the sham group. The inclusion of a sham group is necessary to test the hypothesis because of the large reported placebo effects in OA trials [49]. Treatment with cryoneurolysis is still in its early stage and further studies are needed to determine methodological strategies optimizing its potential therapeutic effects. To achieve long-term pain relief, significant degeneration of the sensory nerves is required. The extent of nerve damage depends on several factors including temperature, contact area, freezing rate, exposure time, thawing strategy and cell type. The current study applies a conservative freezing protocol, that is relatively short ~ 3 min, a single freezing cycle and not at full effect (slower freezing). This might reduce potential risks associated with the procedure but might also attenuate treatment effects. Other studies use up to several cycles and freezing periods up to 10 min, which might induce pain relief for a longer duration due to increased nerve degeneration. These studies, however, tend to focus more on tissue destruction rather than degeneration. Further studies are needed to determine optimal freezing protocols relative to different use cases.

The target nerves, the identification of the target nerves and placement of the cryo probe is equally as important and might have a significant impact on the results. The temperature gradient away from the probe increases drastically [4, 7]. The typical isotherm with the needle (IceSeed 1.5, Galil Medical) used in this study has a temperature of -40 °C in an area equivalent to 11x20mm. Already at 20x27mm the temperature has risen to - 20 °C and at 33x38mm the temperature is up to 0 °C [8]. Thus, to attain temperatures necessary for a relevant impact on sensory nerves for long-term pain relief [-20 °C - 100 °C], probe placement relative to the nerve is crucial. The current study uses a combination of anatomical landmarks, electrical nerve stimulation and ultrasound to accurately determine nerve locations and to account for variation in surrounding anatomical structures. This both increase precision and safety of the procedure. Nevertheless, it is in some cases difficult to identify and differentiate nerve structures with ultrasound which might cause variable results. The procedure is in this study performed by the same surgeon throughout, trained to identify neural structures and to perform cryoneurolysis. In addition, local anesthesia is used locally only at the injection site, 4-6 cm from the 'target' nerve. This allows for continuous feedback on the effect of treatment.

Dissemination of results

The obtained results will be made publicly available within 1 year after the end of the project. This will include publication of the obtained results in international scientific peer-reviewed journals - adhering to the recommendations of the Vancouver convention. Published papers will have open access to ensure a broad distribution and the results will be presented at international scientific conferences. The results will also be presented for the general public and distributed across public platforms (e.g. regional and national press, internet sites, etc.) if copyright allows.

Acknowledgements

Not applicable.

Authors' contributions

The Efficacy of Cryoneurolysis on Chronic Pain in Patients with Knee Osteoarthritis; A Double-blinded Randomized Controlled Sham Trial

Date: 30-09-2024 Clinicaltrials.gov; NCT03774121

Analysis plan

To assess the distribution of continuous outcomes, a visual inspection of the studentized residuals was performed to determine if the assumption of normality was appropriate. Both an Intention-To-Treat (ITT) analysis and a per-protocol (PP) analysis were conducted for all assigned patients. Mixed linear regression with the assumption of unstructured covariance was employed to model the effect of cryoneurolysis treatment over time, accounting for repeated measures by treating individuals as random variables. Fixed effects included time, treatment group, baseline pain levels, and the interaction between group and time, to estimate changes over time. The results are presented as predicted average values and predicted differences between groups, representing the estimated outcomes for each group while considering random effects and covariates included in the model. These are illustrated using marginal effects calculated with the margins command in Stata16. A P-value of less than 0.05 was considered statistically significant. For the primary outcome—average pain over 24 hours on the numeric rating scale—the p-value was adjusted for multiple comparisons (k=9) using the Holm-Bonferroni correction for the mixed effects model. Secondary outcomes were not adjusted, as these were exploratory in nature.

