The patients will be assessed at baseline, 2 weeks post intervention, after completion of GLA:D and 6, 12- and 24- months post cryoneurolysis. The tests will include both patient-reported outcomes (PRO) and objective functional performance tests. The effects of group CRYO and group SHAM will be compared at each timepoint (Table 1).

Primary outcome

The primary outcome is the change in patient reported knee pain intensity assessed using the numeric rating scale (NRS) from baseline to 2 weeks post cryoneurolysis compared between group CRYO and SHAM. NRS consists of an 11-point scale between 0 and 10-, anchored by two verbal descriptors, "no pain" for the score of 0 and "worst pain imaginable" for the score of 10. Respondents are asked to rate their pain intensity on average within the past 24 h. The NRS instrument has been validated in diverse populations and has been widely applied in clinical and research settings [37].

Secondary outcomes

Functional performance will be evaluated by the 30 s chair-stand test, the 40 m fast-paced walk test, the 9-step stair-climb test and isometric knee MVC force [38].

The 30s chair-stand test [39] consists of repeated sitto-stand movement for a duration of 30 s. The starting position is seated, with feet placed flat on the floor, shoulder width apart and with the arms crossed on the chest. The position change to standing, with hips and knees fully extended, followed by sitting back down, with bottom fully touching the seat. The test is performed with usual footwear and the chair should be with a straight back, with no arms, placed against a wall. In cases where the movement cannot be performed even once, the hands are allowed to be placed on the legs or a regular mobility aid can be used - the result is then reported as an adapted test score. The outcome is the total number of complete chair stands performed for the duration of the task (one chair stand represents a stand followed by a sit movement).

[figure not shown]
The 40 m fast paced walk test [40] consists of walking as fast as possible, but still safely, along a 10 m marked walkway, then turning around a cone / tape and return. This is then repeated for a total distance of 40 m. The test is performed with usual footwear and regular walking aid is allowed and recorded. The outcome is expressed as speed. i.e. walking distance (40 m) divided by the time to perform the task (s). Timing is paused during turns.

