The planned number of trial participants is based on the null-hypothesis, assuming no difference between cryoneurolysis treatment and sham. Estimating the sample size for a two-sample means test with a level of significance at 0.05, assuming a common standard deviation (SD) of 3 in NRS pain intensity scores indicates that for the intention-to-treat (ITT) population, 74 individuals is required to obtain a power of at least 80% to establish a minimal clinically important difference (MCID) of 2 in NRS pain scores [47]. The MCID and common standard deviation is based on previous findings with a similar patient group and intervention [48]. With an expected drop-out rate of 20%, a total of 94 individuals will be included in the project, 47 in each group.

Statistical methods

To evaluate the distributions of the continuous outcomes, visual inspection of the studentized residuals will be applied to evaluate whether the assumption of normality is reasonable. Data will be reported as differences between group means (means ± standard deviations, 95% CIs) if normal distributed, otherwise as medians with interquartile ranges. Categorical data will be reported as numbers and proportions. An Intention-To-Treat (ITT) analysis will be used for all allocated patients. Mixed linear regression with the assumption of unstructured covariance will be used to model the effect of the cryoneurolysis treatment over time and to take into account the repeated measures by including individuals as random variables. Time, group of treatment (cryoneurolysis or SHAM) and the Group, time interaction will be used as fixed effects to estimate different patterns of change over time. The results will be illustrated using marginal effects that will be calculated using the margins command of STATA16. If the 95% CIs do not overlap, data will be considered statistically significant. A statistically significant difference of at least two in NRS scores between groups, will be interpreted as a MCID.

Table 1 Timeline of the study – outcomes and variables assessed during the trial period

Timepoint	Study period									
	Enrolment		Allocation	Post-allocation			Follow-up			
	-4w	-1w	0w	2w	10w	na	24w	48w	96w	
Enrolment:										
Eligibility screening	Х									
Informed consent	Х									
Genicular nerve block		Х								
Allocation			Х							
Interventions:										
Cryoeurolysis (CRYO)			Х							
Sham treatment (SHAM)			Х							
GLA:D (SHAM & CRYO)				Х	Х					
Assessments:										

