Pain			Х	Х		Х	Х	Х	Х	
Functional performance			Х	Х		Х	Х	Х	Х	
KOOS			Х	Х		Х	Х	Х	Х	
EQ5D			Х	Х		Х	Х	Х	Х	
Adverse effects			Х	Х		Х	Х	Х	Х	
Analgesics			Х	Х		Х	Х	Х	Х	

w Weeks, na Not applicable (GLA:D start time may vary)

Data monitoring

The current project will not require a formal data monitoring committee. This decision is based on the minimal known risks associated with the intervention and little expected disturbance to the clinical equipoise. Any adverse effects will be recorded and reported according to the guidelines to the Regional Committee on Health Research Ethics for Southern Denmark within 7 days. Once a year the lead investigator will report all expected and unexpected adverse effects that have occurred during that period, with an evaluation of patient safety.

The leading investigators will review the trial processes and data continuously. In addition, a status report will be sent for approval to the Danish Health Authority each year.

Data management

All data will be kept electronically and filed according to a participant code. Data entry will always be handled by the same investigator, who will use unambiguous and standard terminology based on predefined study forms. Complete back-up of all data will be performed regularly and stored on OPEN's servers in the Region of Southern Denmark, using Research Electronic Data Capture (REDCap). REDCap store data via an encrypted connection with restricted access and fulfil the demands for data security. Data will be stored for a duration of 10 years. The project will be reported to the Danish Data Protection Agency and will be handled according to the regulations of the Act on Processing of Personal Data. The full data set will be available to the lead investigators only.

Ethics

The study is conducted according to the declaration of Helsinki and is approved by The Regional Committees on Health Research Ethics for Southern Denmark (S-20180089) registered ClinicalTrials.gov and in (NCT03774121). Given the study design, eligibility criteria and safety measures, the current project does not include special risks for the participating patients. The majority of risks does not require medical attention and serious adverse effects as a result of local anesthetics and cryoneurolysis are very rare. In contrast cryoneurolysis could potentially provide an effective, safe and minimally invasive option to treat pain in OA patients.

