The inclusion of a sham group is necessary to test the hypothesis because of the large reported placebo effects in invasive interventions [49]. In addition, the associated risks are minimal and the nature of misleading, in regards to the administration of the sham trial, will be adequately disclosed and accepted by the patient during the informed consent process. The sham group is implemented according to current standards [50].

Discussion

Impact and significance of the study

Current pain-relieving therapies show small to moderate effects and a significant portion of patients who receive surgery (TKA) report unchanged pain intensity levels post-surgery. This indicates that there is a need for additional therapies that could supplement or improve the existing therapies. A significant difference in the change in pain intensity between sham and intervention post cryoneurolysis treatment would indicate that cryoneurolysis is an effective non-pharmacological therapeutic option to treat pain in OA patients. Outcome measures include both pain, social and psychological factors and functional capacity, which allows for a thorough understanding of treatment effects. The novel addition of GLA:D in combination with cryoneurolysis will elucidate whether feasibility and effectiveness of exercise increase if pain is attenuated and if the potential pain-relieving effects of cryoneurolysis can be extended. The potential benefits include increased functional capacity and quality of life as a result of significant pain relief and improved benefits of physical exercise, ultimately postponing or making surgical intervention unnecessary. This could have a significant impact on patients' lives as well as significant socioeconomic consequences and could change the clinical landscape in the treatment of OA. Finally, an important perspective, is the application of cryoneurolysis in other areas - such as managing pain, related to surgery, to improve rehabilitation.

If the results indicate that cryoneurolysis does not elicit additional pain relief when compared to sham, it might indicate that cryoneurolysis treatment is not suitable for the treatment of OA related pain or at least not in the way it is applied in the current study.

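### Read literally, the SAP's only stated mixed model adjusts function, MVC, KOOS and EQ-5D for baseline pain but not for their own baseline, so their confidence intervals may be wider than the data allow

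*SAP*

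**What the plan says.** The SAP's Analysis plan opens with continuous outcomes in general and then gives a single mixed linear model with unstructured covariance: "Fixed effects included time, treatment group, baseline pain levels, and the interaction between group and time, to estimate changes over time". Its output is described thus: "The results are presented as predicted average values and predicted differences between groups". No separate model is given for secondary outcomes. NRS pain is named only near the end, where multiplicity is discussed.

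The Protocol's Statistical methods section has time, group and their interaction and no baseline covariate: "time interaction will be used as fixed effects to estimate different patterns of change over time".

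The other outcomes do have baselines. In Protocol Table 1 the row "Functional performance" and the rows for KOOS and EQ5D are marked at week 0. Under Secondary outcomes, "Functional performance will be evaluated by the 30 s chair-stand test, the 40 m fast-paced walk test", together with the stair-climb test and isometric knee MVC.

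The documents point both ways on which contrast is reported. The Primary outcome section says "The primary outcome is the change in patient reported knee pain intensity", and the Discussion speaks of "A significant difference in the change in pain intensity between sham and intervention post cryoneurolysis treatment". The Outcomes section, however, has the two arms compared at every visit. Neither document says whether the baseline visit is a row of the response, or whether the arms share a baseline mean.

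**The concern.** For a continuous outcome measured before and after randomization, its own baseline is usually the strongest available predictor of follow-up. Baseline pain may be a weak stand-in for, say, quadriceps force or walking speed. Leaving the own baseline out does not bias a randomized comparison, but it can leave explainable variance in the error term and widen the interval.

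How much is lost depends on how the model was set up, and three set-ups fit the text:

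- **A.** Follow-up values are compared, adjusted for baseline pain only.
- **B.** Baseline is a response row, each arm has its own baseline mean, and change is contrasted.
- **C.** Baseline is a response row with one mean common to both arms, which already uses the own baseline fully.

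The change wording in both documents makes B at least as plausible as A. At stake is the width of the intervals for the exploratory outcomes, and whether a reader can tell which contrast a reported secondary difference represents.

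**Working it through.** **1. The plan's own figure.** Protocol, Sample size: difference 2, SD 3, significance level 0.05 (taken as two-sided), power 80%. A two-sample t test gives power 0.797 with 36 per arm and 0.808 with 37, so 74 in total reproduces. With 20% dropout, 74/0.8 = 92.5, hence 93, or 94 for equal arms. This rests on NRS pain alone and nothing below changes it. I use its 37 per arm. In SD units the unadjusted SE is √(2/37) = 0.2325, and the 95% half-width is 1.96 × 0.2325 = 0.456.

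**2. Set-up B (change contrasted).** Let r be the assumed correlation of an outcome with its own baseline. Residual variance is 2(1 − r) for change and 1 − r² with own-baseline adjustment, so the SE ratio is √((1 + r)/2).

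| r | Half-width, change | Half-width, own baseline | SE ratio | Cut |
|---|---|---|---|---|
| 0.5 | 0.456 | 0.395 | 0.866 | 13% |
| 0.7 | 0.353 | 0.325 | 0.922 | 8% |
| 0.8 | 0.288 | 0.273 | 0.949 | 5% |

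Turned round, the change SE is 1/0.866 = 1.155 to 1/0.949 = 1.054 times the adjusted one, that is, 15% to 5% larger than needed.

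**3. Set-up A (follow-up compared, pain-only adjustment).** Let ro be the correlation with own baseline, rp the correlation with baseline pain, and c = 0.3 the correlation between the two baselines (all assumed). With both covariates, R² = (ro² + rp² − 2·ro·rp·c)/(1 − c²). Adding own baseline multiplies the SE by √((1 − R²)/(1 − rp²)); swapping it for pain multiplies the SE by √((1 − ro²)/(1 − rp²)).

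| (ro, rp) | Adding own baseline | Replacing pain |
|---|---|---|
| (0.5, 0.4) | 0.90 | 0.94 |
| (0.7, 0.3) | 0.74 | 0.75 |
| (0.8, 0.2) | 0.61 | 0.61 |
| (0.3, 0.3) | 0.97 | 1.00 |
| (0.3, 0.4) | 0.98 | 1.04 |

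The last two rows show that the gain is small when own baseline predicts no better than pain, and that replacing pain can then cost 4%. If own baseline adds nothing beyond pain, including it costs one degree of freedom per visit: 74 − 2 − 1 = 71 falls to 70, and √(71/70) = 1.007, about 0.7% of the SE.

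**4. Set-up C, and whether repeated measures alone would be enough.** A generalized least squares calculation was made with six visits, complete data, equal correlation between visits (assumed) and no pain covariate. The SEs at the first follow-up were:

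| r | Change, arms free at baseline | Common baseline mean | Own-baseline formula |
|---|---|---|---|
| 0.5 | 0.2325 | 0.2013 | 0.2013 |
| 0.7 | 0.1801 | 0.1660 | 0.1660 |
| 0.8 | 0.1470 | 0.1395 | 0.1395 |

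Putting baseline in the response recovers full precision only when the arms are given a common baseline mean. Neither document states that constraint.

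**5. Is one own-baseline slope enough?** Suppose correlation decays by a factor of 0.8 per visit step (assumed, complete data, 37 per arm). Baseline then correlates 0.8⁵ = 0.328 with the fifth follow-up. The SEs at that visit are:

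- No baseline adjustment: 0.232.
- Slope free at each visit, or common baseline mean: 0.2325 × √(1 − 0.328²) = 0.220.
- One slope for all visits: the fitted slope settles at about 0.69. Residual variance is 1 − 2(0.69)(0.328) + 0.69² ≈ 1.024, so the SE is 0.2325 × √1.024 = 0.235.

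A single common slope can therefore do slightly worse at the last visit than no adjustment at all.

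**The case against.** The strongest reply is that this is an ambiguity in a short paragraph, not a demonstrated fault. Pain is the only outcome the paragraph names, so the baseline-pain term may be shorthand for the baseline of the outcome analysed. Under that reading, or under C, nothing is lost. The large gains in step 3 need set-up A together with a high own-baseline and a low pain correlation. The outcomes are exploratory, and the SAP is in the past tense, so a re-analysis adds a second, post hoc set of estimates.

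Most of this stands, and it limits the point to a conditional one. It does not remove it: the model sentence follows an opening about continuous outcomes generally, nothing says the covariate changes with the outcome, and the Protocol does not fill the gap.

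Three stronger readings are tempting and not supported:

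- A reader might infer that the secondary estimates are biased. Randomization protects them whether or not the covariate is used.
- A reader might take the SAP's closing remark that secondary outcomes were not adjusted as confirming that no baseline was used. It follows the Holm-Bonferroni sentence and concerns multiplicity.
- A reader might infer that a quarter or more of the precision was certainly lost. No correlation is given, and which set-up was used is unknown.

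**Conclusion.** The point holds in conditional form. Followed literally, the stated model passes over baseline values that the trial schedules for collection. The likely size is modest if change was contrasted, potentially large if follow-up values were compared with only pain adjusted, and zero under a common baseline mean or the shorthand reading. All sizes rest on assumed correlations, 37 per arm and complete data. Only the intervals of exploratory outcomes are touched: the primary NRS model already has its own baseline as covariate, and the sample size was set on NRS pain alone. This merits a change or a clarification, but it does not threaten the trial's main conclusion.

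**What to change.** For each continuous secondary outcome, do one of the following; baseline pain may stay in the model either way.

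- Add the outcome's own week-0 value together with a baseline-by-time interaction, and model the post-baseline visits.
- Keep baseline as a response row under the unstructured covariance, with a baseline mean common to both arms.

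A single common-slope baseline covariate should not be treated as equivalent to these, for the reason in step 5. No change to the primary NRS model is asked for.

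State for each outcome, NRS pain included, which baseline covariate was used and whether the baseline visit was a response row. If own baselines were already used, that statement is enough.

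The cost is a sentence per outcome, a little extra analysis and a few degrees of freedom, with no new data. Because the SAP reports its analyses as done, any re-analysis of secondary outcomes should be labelled as specified afterwards.

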In Denmark, a standardized education and neuromuscular exercise program (GLA:D) has been implemented in the national clinical guidelines by the Danish Health Authority, for the treatment of knee and hip OA in clinical practice [29]. Recent studies show that exercise reduce pain and improve function in people with knee or hip OA [30, 31]. Despite of these reports, the beneficial effects remains moderate with difficulties in maintaining these effects at long-term follow-up [29]. In addition the implementation of the exercise program is not optimal [12] and includes a significant discontinuation rate for patients reporting high pain levels [29]. In this line, pain and muscle weakness, among others, have been reported to be major barriers for physical exercise [32, 33]. The application of cryoneurolysis treatment as an effective pain reducing treatment prior to GLA:D might provide significant pain relief and improve patients' ability to produce force, resulting in improved adherence, exercise effectiveness and long-term benefits [34]. Currently, no studies have reported the effects of cryoneurolysis treatment on pain and functional performance in conjunction with a standardized education and exercise programme (GLA:D), in patients with knee OA.

Objective

The primary objective of this RCT is to investigate if cryoneurolysis is superior to sham at decreasing pain intensity 2 weeks after the intervention in patients with painful knee OA.

The secondary objective is to explore the safety and effectiveness of cryoneurolysis followed by GLA:D and to assess long term effects.

Methods

This study protocol describes the design of an ongoing parallel-group RCT conducted at the Department of Neurology, University Hospital of Southern Denmark, Esbjerg, Denmark. The study protocol conforms to the Standard Protocol Items: Recommendations for Interventional Trials (SPIRIT) (see also appendix, Table 2), and The Consolidated Standards of Reporting Trials of Nonpharmacological Treatments (CONSORT NPT) will be used as a guideline for reporting this trial. The study is conducted according to the declaration of Helsinki and is approved by The Regional Committees on Health Research Ethics for Southern Denmark (S-20180089) and registered in ClinicalTrials.gov (NCT03774121).

Participants and recruitment procedure

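### The 2-week primary contrast is sized at two-sided 0.05, but the SAP applies Holm-Bonferroni over nine unlisted comparisons, so its threshold and power cannot be worked out from the plan

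*SAP*

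**What the plan says.** The protocol sets a single primary question. Its Objective section states: "The primary objective of this RCT is to investigate if cryoneurolysis is superior to sham at decreasing pain intensity 2 weeks after the intervention". The Primary outcome section agrees: "The primary outcome is the change in patient reported knee pain intensity assessed using the numeric rating scale (NRS) from baseline to 2 weeks", compared between the two arms. Effects on pain over the rest of the 24 months are described in the Abstract as exploratory.

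The Sample size section begins "Estimating the sample size for a two-sample means test with a level of significance at 0.05". With a common SD of 3 and a difference of 2 NRS points it arrives at 74 patients for at least 80% power, then 94 after a 20% drop-out allowance. It makes no allowance for multiplicity.

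The SAP's general threshold is p below 0.05. For the primary outcome it adds that "the p-value was adjusted for multiple comparisons (k=9) using the Holm-Bonferroni correction for the mixed effects model". It does not mention the 2-week time point, list the nine comparisons, or exempt any contrast. On the model it says: "Fixed effects included time, treatment group, baseline pain levels, and the interaction between group and time".

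The protocol's Statistical methods section has a different rule: "If the 95% CIs do not overlap, data will be considered statistically significant". The SAP does not repeat it.

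**The concern.** A sample size describes the power of a trial only if the test is run at the alpha used to derive it. Here one contrast was sized at 0.05, and the later plan appears to place it in a Holm family of nine. Under Holm, the threshold for any one test depends on the rank of its p-value among all nine, so a reader needs the list to know what the primary result must achieve.

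Two things are at stake. The trial may miss a real effect on the only question it was powered for. The primary result may also turn on comparisons that nobody outside the trial can identify. For example, a 2-week p-value of 0.01 fails if it is the smallest of the nine (threshold 0.0056). It passes if it is the sixth smallest, behind five that have already passed (threshold 0.0125).

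**Working it through.** **Inputs.** From the protocol's Sample size section: difference 2, SD 3, alpha 0.05, 74 evaluable (37 per arm), 94 randomised (47 per arm). From the SAP: Holm, k = 9. Sidedness is not stated. A one-sided test would need about 2 × (1.645 + 0.842)² × 9/4 = 27.8, so 28 per arm or 56 in all; the stated 74 therefore implies a two-sided test. The drop-out rate is not tied to week 2, so the number analysed there may lie anywhere from 74 to 94.

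**1. Reproduce the plan's figure.** For a two-sample t test, SE = 3 × √(2/n), the noncentrality is 2/SE, and df = 2n − 2.
- n = 37: SE = 0.697, noncentrality 2.87, power 80.8% at 0.05. At n = 36 it is 79.7%. So 37 per arm, 74 in all, is reproduced.
- Drop-out: 37/0.8 = 46.25, so 47 per arm and 94 in all.

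**2. Holm thresholds.** The j-th smallest of nine p-values is compared with 0.05/(10 − j), stopping at the first failure: 0.0056, 0.00625, 0.0071, 0.0083, 0.01, 0.0125, 0.0167, 0.025, 0.05. A 2-week p-value at or below 0.05/9 always passes, because any smaller p-value also passes. One above 0.05 always fails. Power under Holm is therefore bounded by the power at these two alphas.

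| Per arm | Power at 0.05 | Power at 0.05/9 | Smallest significant difference at 0.05 | at 0.05/9 |
|---|---|---|---|---|
| 37 | 80.8% | 50.7% | 1.39 | 1.99 |
| 47 | 89.2% | 65.2% | 1.23 | 1.76 |

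The smallest significant difference is the critical t times SE; for n = 37 at 0.05/9, 2.859 × 0.6975 = 1.99, almost the MCID of 2. Reaching 80% at 0.05/9 would need 61 per arm.

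**3. The whole Holm procedure.** This was simulated with nine two-arm t tests on patient-level data, with assumed correlations between tests of 0 to 0.7. Power for the 2-week contrast:

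| Comparisons with a difference of 2 | 37 per arm | 47 per arm |
|---|---|---|
| 2-week contrast only | 51% | 65-66% |
| Five of nine | 54-55% | 69-70% |
| All nine | 61-63% | 76-80% |

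The last row is not a ceiling. If other members of the family had larger effects than 2, power would move further towards the 0.05 column of the first table.

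**4. Baseline adjustment.** The SAP's model includes baseline pain. With correlation r between baseline and 2-week scores, the residual SD is 3 × √(1 − r²), with one df lost. The documents give no r. At an assumed r = 0.5 the SD is 2.60. Power at the strictest step is then 67% (37 per arm) and 81% (47 per arm), against 90% and 96% at 0.05. The strictest step reaches 80% only at r of about 0.64 (37) or 0.48 (47).

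**5. Does k = 9 follow from the visit schedule?** The Outcomes section says: "The patients will be assessed at baseline, 2 weeks post intervention, after completion of GLA:D and 6, 12- and 24- months post cryoneurolysis". That is five post-baseline visits and so five between-arm contrasts, not nine.

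**6. Side note on the protocol's interval rule.** If it means two group intervals, with equal SEs they separate only when |z| > 2 × 1.96/√2 = 2.77, a two-sided alpha of about 0.0056. Power is about 51% and 65% with separate t intervals, or 54% and 68% with a pooled SD and normal intervals, which is closer to margins from one mixed model.

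**The case against.** The strongest reply is that Holm is valid and conservative, that dependence on the other p-values is how it works, and that its first step is not the threshold actually applied. All of that stands. A reader might infer that the primary contrast is tested at 0.0056 and that the trial has 51% power. The documents do not support this: 0.0056 is the strictest of nine steps, the SAP's model adjusts for baseline, and up to 94 patients may be analysed. The figures of 51% and 65% are floors on the protocol's inputs.

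A second reply is that the 2-week contrast may lie outside the nine, in which case the SAP's threshold for it is already 0.05. The text does not exclude this, although a correction stated for the primary outcome points the other way. For the same reason, it cannot be said flatly that testing the contrast alone at 0.05 would be looser than the SAP.

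Third, a reader might take the protocol's non-overlap rule as a second rule in force. The SAP's p-value rule appears to replace it, though neither document says so. The protocol also does not state which intervals are meant. The word overlap and the use of group margins favour two group intervals, but this remains a reading.

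Fourth, one could explain nine as the model's group (1), time (4) and interaction (4) coefficients. The SAP does not say this, the count leaves out the baseline covariate, and time coefficients do not compare the arms. Nothing here rests on it.

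Finally, the protocol does name the 2-week time point, so its absence from the SAP is not by itself a gap. What the protocol cannot supply is the family of nine and whether the 2-week contrast belongs to it.

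**Conclusion.** The point holds as a mismatch between sizing and testing, and as a family of comparisons left undefined. If the 2-week contrast is among the nine, its threshold lies between 0.0056 and 0.05, and the stated 80% does not describe its test. Without baseline adjustment, power lies between 50.7% and 80.8% with 74 analysed, and between 65.2% and 89.2% with 94. Where it falls depends on comparisons that the plan does not list. Baseline adjustment raises these figures by an amount the documents do not allow one to fix.

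The conclusion assumes a difference of 2, SD 3, a two-sided test, and that the contrast is in the family. It does not imply inflated type I error or a biased estimate, and the effect estimate is unaffected. This should be fixed, because the decision on the main question may depend on the missing list.

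**What to change.** In the SAP:
- Name the baseline-adjusted CRYO minus SHAM difference in NRS at 2 weeks as the primary contrast.
- List the nine comparisons and say whether this contrast is one of them.
- Report its unadjusted and Holm-adjusted p-values side by side.
- If the correction applies to it, restate the power. Give the first-step figure (about 51% with 74 analysed, 65% with 94) as a floor, and any baseline-adjusted figure with its assumed correlation.
- If it is tested alone at two-sided 0.05, say so. If that departs from the SAP's Holm family, state when and why it was decided relative to unblinding.
- State that the p-value rule replaces the protocol's interval rule, and do not restore the latter.

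The cost is a list, a few sentences and one extra p-value; no new data are needed. If the correction is kept, the stated power is less favourable. If it is dropped for the primary contrast and no other family is kept, pain at later visits loses formal multiplicity protection, but the protocol treats those results as exploratory.
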